## 13.5 Methods of Analysis

The 2-year-EFS rate and its one sided 95%-confidence interval with the fixed upper bound of 1 will be calculated. If the one sided 95%-confidence interval does not include p0 = 0.5, the experimental treatment is considered effective.

## 13.6 Interim Analysis

No interim analysis is planned.

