### 4.5 Number of Study Participants

18 subjects will be enrolled in the study

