### Further safety examinations

A regular toxicity assessment will be obtained as outlined in the study evaluations (7.4) and in chapter 10. Furthermore, the primary endpoint of this trial, event-free survival is a combined efficacy and safety endpoint and will therefore also be used for the assessment of safety.

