## **13.3 Sample Size Calculation**

The primary endpoint is a binary variable indicating event-free-survival at 2 years. The reference 2year-EFS rate was obtained from data of the SAL study group including 104 patients with t(8;21). Of the 104 patients, 78 did neither display FLT3-ITD nor c-KITmut. Eight patients were FLT3-ITD positive and 18 patients displayed a c-KIT mutation.

Reference 2-year-EFS rate of a historical cohort: p0 = 0.5Success rate of interest: p1 = 0.8Difference between reference and success rate of interest:  $\delta = 0.3$ nullhypothesis:  $p \le p0$ alternate hypothesis:  $p \ge p1$ power: 80% significance level: 5% one sided The nullhypothesis of this trial is that the 2-year-EFS rate is worse or equal to 0.5 under the experimental treatment. The alternate hypothesis is that the 2-year-EFS-rate is equal to 0.8 or greater. In an exact single stage phase 2 design 18 patients have to be enrolled to be able to detect the critical difference in the EFS-rates of 0.3 with a power of 80% and a one-sided significance level of 5%. The nullyhpothesis can be rejected if after 2 years 13 or more of 18 patients are without an event. The calculation is based on the exact binomial distribution as described in A'Hern [27].

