## 14 Data Safety Monitoring Board (DSMB)

The DSMB will consist of three members of the scientific community not involved in this trial. The committee will meet to review study data with the National Coordinating Investigator (LKP) of the trial and review all serious adverse events (SAE), and suspected unexpected severe adverse reactions (SUSARs). Meetings will take place approximately every 4-6 months and will receive monthly SAE listings from the safety database between meetings for review as well. The DSMB will give recommendations about the continuation of the trial and/or about necessary trial amendments.

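### No EFS event count or threshold is set for the DSMB, so nothing in the protocol prompts an enrolment pause once a 6th event puts 13 of 18 out of reach

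*Protocol*

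**What the plan says.** The trial is a single-stage design. Section 4.5 states that "18 subjects will be enrolled in the study". Section 13.3 sets p0 = 0.5, p1 = 0.8 and "significance level: 5% one sided", and allows rejection if after 2 years "13 or more of 18 patients are without an event". Section 13.5 gives the same decision as an interval: "If the one sided 95%-confidence interval does not include p0 = 0.5, the experimental treatment is considered effective".

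On looking at data during the trial, section 13.6 says "No interim analysis is planned"; the synopsis and the timetable in 4.2 agree. Under section 14 the DSMB meets about every 4 to 6 months, looks at data from the study with the coordinating investigator, and is to "review all serious adverse events (SAE), and suspected unexpected severe adverse reactions (SUSARs"). It also receives monthly SAE listings and advises on continuation. EFS events are not named there and no threshold is given.

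Section 9.2, under further safety examinations, states that "event-free survival is a combined efficacy and safety endpoint and will therefore also be used for the assessment of safety". It does not say who reviews EFS for that purpose, or when.

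**The concern.** The rule tolerates at most 5 failures among 18 patients. Accrual is planned over 48 months against a 24-month endpoint, and primary treatment failure is called 35 days after the start of the second induction (13.2.1). A 6th event can therefore occur while patients are still entering. From then on new patients cannot change the primary test result, and the protocol contains nothing that brings this to anyone's attention.

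SAE reporting fills the gap only in part. Deaths reach the DSMB as SAEs. Primary refractory disease and relapse are not in themselves among the SAE criteria in 10.1.2, and 10.2.2 takes several consequences of AML progression out of expedited reporting. These two non-fatal failures are the ones that 13.2.1 gives as the reason for choosing EFS.

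**Working it through.** **Inputs.** n = 18 (4.5); cut-off 13, p0 = 0.5, p1 = 0.8, one-sided 5% (13.3); interval rule (13.5); exclusion of patients whose 2-year status cannot be evaluated (13.4); accrual 1 May 2012 to 30 April 2016, i.e. 48 months (4.2).

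**The protocol's own figure.** With X event-free patients out of 18:

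- P(X ≥ 13 | 0.5) = (8568 + 3060 + 816 + 153 + 18 + 1) / 2^18 = 12616 / 262144 = 0.0481.
- P(X ≥ 13 | 0.8) = 0.867.
- n = 18 is the smallest size with type I error ≤ 0.05 and power ≥ 0.80 (n = 17 gives power 0.758).
- The exact one-sided 95% lower limit is 0.502 for 13/18, so the count rule and the interval rule agree.

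The sample size calculation is reproduced.

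**After 6 events.** At most 18 − 6 = 12 patients can be event-free. Then p = (12616 + 18564) / 262144 = 0.119 and the lower limit is 0.446, which leaves 0.5 inside the interval. Excluding non-evaluable patients does not help. A patient with an event within 2 years is evaluable, so the six stay in, and the failures allowed are 4 at n = 16 or 17 and 5 at n = 18. Six are compatible with rejection only from n = 21.

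**Error rates with a pause at the 6th event.** Rejection needs 5 or fewer events and the pause needs 6 or more. The two cannot occur in the same trial, so 0.0481 and 0.867 are unchanged whether enrolment then stops or resumes.

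**How often it would act.** The protocol gives no accrual pattern or event-time distribution, so these are assumptions: 18 evenly spaced entries over 48 months, exponential event times with the stated 2-year EFS rate, only events within 24 months counted, and a lag from event to action of 0 or 5 months. The mean is taken over all simulated trials, including those with no later entry.

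| True 2-year EFS | P(≥ 6 events in 18) | Pause before last enrolment, lag 0 / 5 months | Mean enrolled afterwards, lag 0 / 5 months |
|---|---|---|---|
| 0.5 | 0.952 | 75% / 60% | 3.3 / 2.0 |
| 0.6 | 0.791 | 48% / 32% | 1.7 / 0.9 |
| 0.7 | 0.466 | 20% / 11% | 0.6 / 0.3 |
| 0.8 | 0.133 | 4% / 2% | 0.1 / below 0.1 |

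Sensitivity at a true rate of 0.5:

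- 3-month lag: 67% and 2.5 patients.
- No lag, random instead of even entry: 69% and 2.8 patients.
- No lag, even entry, 30% of failures at about day 35: 82% and 4.1 patients.
- No lag, accrual completed in 24 months: 38% and 1.0 patient.

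**The case against.** The strongest reply is that nothing here is wrong. A single-stage design without an interim analysis is legitimate, the calculation is right, the absence of an interim look is stated consistently, and the content of DSMB listings is often left to a charter. All of that stands, and the point is rated accordingly.

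Three stronger readings are tempting, and the protocol supports none of them.

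- A reader might infer that enrolment is meant to continue after the 6th event. No section says so; there is only no prompt to pause.
- A reader might infer that the DSMB cannot see EFS. Its remit covers study data in general and it advises on continuation. The trial is open-label, EFS events end study treatment (6.3), and the central study office confirms each registration (6.2). People who could act are in place.
- A reader might infer that six events show the regimen does not work. Six of 18 still leaves 12/18 = 67% event-free, above the reference of 0.5. At true rates of 0.6 and 0.7, six or more events occur in 79% and 47% of trials.

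It is also fair to object that only the reject-or-not decision is settled at that point. The 2-year EFS rate with its interval, and the secondary, MRD and toxicity results, still gain from every patient in a rare disease. This stands, and it is the reason to make the rule advisory.

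**Conclusion.** The point holds as a minor, inexpensive improvement. That a 6th event within 2 years makes success impossible is exact and needs no assumption beyond the planned 18 patients. That the protocol names no EFS count or threshold follows from 13.6 and 14, and it fits poorly with the statement in 9.2 that EFS also serves the safety assessment.

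The benefit depends on assumed timing. If the regimen is no better than the reference, about 2 to 3 of 18 patients on average would be enrolled after the test is settled under 48-month accrual, and about 1 if accrual took 24 months. If the regimen performs as hoped, the pause would almost never act during accrual. At intermediate rates of 0.6 to 0.7 it would sometimes fall on a regimen that is better than the reference, so it should not be an automatic stop.

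**What to change.** In sections 13.6 and 14, add:

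- The count of confirmed EFS events is part of each DSMB listing.
- If the 6th EFS event within 2 years of inclusion is confirmed during accrual, enrolment pauses for a DSMB recommendation, which is non-binding. Patients already enrolled continue as planned.
- If accrual stops, the 2-year EFS rate is reported with its exact interval for the patients enrolled, described as stopped early, and the null hypothesis is not rejected.

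This takes a few lines and uses meetings that are already scheduled. It leaves type I error and power as they are, provided that only confirmed events within the 2-year window count. If the board advises stopping, the price is a less precise primary estimate and fewer patients for secondary, MRD and safety data.

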## 14 Data Safety Monitoring Board (DSMB)

The DSMB will consist of three members of the scientific community not involved in this trial. The committee will meet to review study data with the National Coordinating Investigator (LKP) of the trial and review all serious adverse events (SAE), and suspected unexpected severe adverse reactions (SUSARs). Meetings will take place approximately every 4-6 months and will receive monthly SAE listings from the safety database between meetings for review as well. The DSMB will give recommendations about the continuation of the trial and/or about necessary trial amendments.

## **15 Subsequent Amendments to the Protocol**

### 15.1 Compliance with the Protocol

The investigator should conduct the clinical trial in compliance with this protocol. For this purpose, the document will be signed by the sponsor and the investigator. As a general rule, the investigator should not deviate from the protocol or make amendments to the protocol without the agreement of the sponsor/authority/ethics committee (unless subject safety is at risk, see below).

Any deviations from the approved protocol should be documented and explained by the investigator or an individual who is designated by the investigator.

The investigator may deviate from the protocol or make an amendment to the protocol without prior approval of the ethics committee to eliminate immediate risks to the trial subjects. The deviation or amendment should subsequently be reported to the ethics committee, the sponsor and, if necessary, the competent authority, giving reasons.

## 15.2 General Amendments to the Protocol

The sponsor can make general amendments to the protocol after the clinical trial has started. These may be of an administrative nature (logistical/administrative amendments) or substantial (subject to approval).

## **16 Ethical and Legal Principles**

## 16.1 Subject Informed Consent

Before enrolment in the clinical trial, the subject will be informed that participation in the clinical trial is voluntary and that he/she may withdraw from the clinical trial at any time without having to give reasons and without penalty or loss of benefits to which the subject is otherwise entitled.

The treating physician will provide the subject with information about the treatment methods to be compared and the possible risks involved. At the same time, the nature, significance, implications, expected benefits and potential risks of the clinical trial and alternative treatments will be explained to the subject. During the informed consent discussion, the subject will also be informed about the insurance cover that exists and the insured's obligations. The subject will be given ample time and opportunity to obtain answers to any open questions. All questions relating to the clinical trial should be answered to the satisfaction of the subject and/or his/her legal representative. In addition, the subject will be given a "Subject Information Sheet" which contains all the important information in writing.

The subject's written consent must be obtained before any study-specific tests/treatments.

For this purpose, the written consent form will be **personally dated and signed** by the trial subject and the investigator conducting the informed consent discussion.

By signing the consent form, the subject agrees to voluntarily participate in the clinical trial and declares his/her intention to comply with the requirements of the clinical trial and the investigator's instructions during the clinical trial. By signing the form, the subject also declares that he/she agrees to the recording of personal data, particularly medical data, for the study, to their storage and codified ("pseudonymised") transmission to the sponsor, to the competent authority, and further

agrees that authorised representatives of the sponsor Technische Universität Dresden, who are bound to confidentiality, and national or foreign competent authorities may inspect his/her personal data, particularly medical data, which are held by the investigator.

After signing, the subject will be given one copy of the signed and dated written consent form and any other written information to be provided to the subjects.

In the case of substantial amendments, the subject must be informed with an appropriate revised subject information/consent form. Changed study procedures can only be carried out if they have been approved by the competent authority and the leading Ethics Committee, and if the subject has been appropriately informed and has given his/her written consent.

## 16.2 Ethical and Regulatory Requirements

A favourable opinion from the competent ethics committee and the approval of the competent authority must be obtained before a clinical trial is started:

## 16.2.1 Ethics Committee/ Competent Authority

Before this clinical trial is started, the sponsor will apply for the following, according to the applicable legal requirements:

- Favourable opinion from the competent ethics committee'
- Approval of the competent supreme federal authority

### 16.2.2 Additional Requirements Concerning the Notification of Authorities

The following other notification requirements apply at the start and end of the study (for reporting requirements during the study, see section 10.2.1 (investigator) and 10.2.2 (sponsor):

Notification by the sponsor:

- According to section 67, para. 1 AMG, the sponsor will notify the competent authority and the local authority of the clinical trial before it is started. The notification will include details of the sponsor and details of all investigators, indicating their position as principal investigator or coordinating investigator if necessary.
- According to section 13, para. 8 GCP-V, the sponsor will notify the competent authority, the local authority and the competent ethics committee of the end of the clinical trial within 90 days. If the clinical trial was terminated or suspended by the sponsor, notification will occur within 15 days, giving reasons for the termination or suspension.

### Notification by the investigator

- According to section 67, para. 1 AMG, the investigator will notify the competent authority\* and the local authority of the clinical trial before it is started. The investigator can assign the task of notification to the sponsor and must document this in an appropriate manner (section 12 (3) GCP-V) data (section 12, GCP-V).
- The investigator will notify the local authority of the end of the clinical trial within 90 days. The investigator can assign the task of notification to the sponsor and must document this in an appropriate manner (section 12 (3) GCP-V).

### 16.4 Data Protection and Confidentiality

The trial subjects will be informed of the purpose and extent of the collection and use of personal data, particularly medical data (see section 16.1).

For the protection of these data, organisational measures have been taken to prevent disclosure to unauthorised third parties. For example, the subject data will be captured in pseudonymized form (subject ID No. for the particular study, age at study entry) throughout the documentation and evaluation phase.

## 17 Study Documents and Filing

## 17.1 Study Documents/Investigator Site File

The investigator will be given an investigator site file containing all the necessary essential study documents for the initiation of the trial at his/her centre. The essential documents include a list on which the investigator will enter all appropriately qualified persons to whom he/she has delegated important trial-related tasks.

The investigator, or an individual who is designated by the investigator, will be responsible for the maintenance and completeness of the study documents during the clinical trial. At the request of the sponsor, monitor, auditor, ethics committee or competent authority(ies), the investigator shall make available all the requested study-related records for direct access. Essential documents must not be removed permanently.

## 17.2 Archiving

After completion of the clinical trial, the essential study documents - as defined by section 8 of the Guideline ICH E6 for Good Clinical Practice (GCP) - from clinical trials will be retained at the study centre for a sufficient period so that they will be available for audits and inspections by the authorities.

The investigator will be responsible for the storage. The following retention periods will apply after the completion/termination of the clinical trial:

- The above-mentioned essential documents must be retained for at least 10 years (section13, para. 10 GCP-V); the identification codes of studies submitted for drug approval must be retained for at least 15 years (2001/83/EC).
- The medical records and other source documents must be retained for the longest possible period allowed by the hospital, the institution or the private practice.

The investigator/the institution should take measures to prevent accidental or premature destruction of these documents.

The sponsor will notify the investigator in writing when the study-related essential documents are no longer required.

## **18 Administrative Agreements**

## 18.1 Financing of the Study

## 18.1.1 Study Agreeement/Investigator Compensation

According to ICH-GCP 4.9.6, a study agreement on the conduct of the clinical trial and the compensation for conducting the trial will be signed between the sponsor (donor) of the clinical trial and the investigators including their heads of administration (donee).

### 18.1.2 Reimbursement of Trial Subjects

Trial subjects will not be compensated.

### 18.2 Study Language

Entries should be made on the case report form and the study forms (ISF) in German language.

## 18.3 Publication

The right of publication rests primarily with the sponsor, the coordinating investigator and the other investigators involved. All data collected in connection with the clinical trial will be treated in confidence by the sponsor/coordinating investigator and all others involved in the study, until publication. Interim data and final results may only be published (orally or in writing) with the agreement of the sponsor Technische Universität Dresden, the coordinating investigator and the other investigators. This is indispensable for a full exchange of information between the above-named parties, which will ensure that the opinions of all parties involved have been heard before publication. The agreement, which does not include any veto right or right of censorship for any of the parties involved, may not be refused without good reason.

## **19** Appendix 1: Relevant Guidelines and Laws

List and reference to websites or copy texts in directly

- Declaration of Helsinki
   http://www.wma.net/e/policy/b3.htm
- ICH-GCP Guidelines http://www.ich.org
- EMEA Guidelines http://www.emea.eu.int/index/indexh1.htm
- AMG/GCP-V etc.: http://www.bfarm.de/cln\_043/nn\_666970/DE/Arzneimittel/klinPr/klin\_prf\_genehm/gestexte-verordnungen.html
- Common Terminology Criteria for Adverse Events v3.0 (CTCAE)
   Source: http://ctep.cancer.gov/forms/CTCAEv3.pdf

A hard copy version of this document is enclosed separately.

## 20 Appendix 2: Examples of Inducers and Inhibitors of CYP3A4

Inhibitors**
Amiodarone
Cimetidine
Clarithromycin
Clotrimazole
Cyclosporin
Erythromycin
Fluconazole (doses >200 mg)
Fluoxetine
Grapefruit Juice
Indinavir
Itraconazole
Ketoconazole
Metronidazole
Mibefradil
Miconazole
Nefazodone
Nelfinavir
Norfloxacin
Quinine
Ritonavir
Saquinavir
Sertraline
Zafirlukast

This is not a comprehensive list of inducers and inhibitors of CYP3A4 and is meant only to be used as a guide. This web site may also be consulted http://medicine.iupui.edu/flockhart/table.htm

\*Note: Inducers of CYP3A4 may result in rapid metabolism of midostaurin and a decreased clinical effect. \*\*Note: Inhibitors of CYP3A4 may result in delayed metabolism of midostaurin and increased side effects.
